## **3 STUDY DESIGN AND EVALUATION**

### **3.1 Study Design**

A prospective, randomized, open-label, multicenter, parallel, observational study to compare the safety and efficacy of brand versus generic tacrolimus in 200 kidney transplant recipients over a one-year follow up period. All subjects will receive other immunosuppressive medications including induction therapy (thymoglobulin, basiliximab, or no induction) and maintenance, including mycophenolate mofetil and corticosteroid therapy as directed by standard-of-care at each center. Their medication information will be recorded in their study files.

The Phase 1 portion of this study consist of 2 Arms:

Arm 1: Brand Tacrolimus (Prograf) for entire study duration (12 months)

Arm 2: Generic Tacrolimus for entire study duration (12 months)

Additionally, the study consists of 2 Phases:

Phase 1: Subjects have been randomized into either Arm 1 or Arm 2 medication. Once 40 subjects have been enrolled onto Phase 1, Phase 2 will commence.

Phase 2: Subjects will no longer be randomized. All subjects will be enrolled onto generic tacrolimus because they have elected to receive generic tacrolimus (standard of care from the subject's insurance).

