### 3.4 Sample Size Determination

The total number of subjects (200) is based on statistical calculation to have more than 80% power to detect a non-inferiority margin of 26 percentage points of the composite endpoint of acute rejection, graft loss and death over the baseline of 13% in the brand tacrolimus at one year post-transplantation. (See details in next paragraph.)

For power considerations regarding the primary objective, the following assumptions are made:

1. Subjects will be uniformly enrolled over 1-year accrual period
2. Primary analysis will be done via non-inferiority, log-rank tests on an intention-to-treat basis comparing generic recipients (Arm 2) with brand recipients (Arm 1)
3. Data will be also collected from standard-of-care records on subjects who are lost to follow-up
4. Overall, 13% of subjects are expected to experience the primary endpoint by 1 year post-transplant, yielding a yearly hazard rate for the reference group of  $-\log(0.87) = 0.14$

Given these assumptions, 200 subjects (if 50 and 150 in brand and generic groups, respectively) are needed to observe 25 events (6 and 19 in brand and generic groups, respectively). These numbers achieve >80% power at a 0.05 significance level to detect a non-inferiority hazard ratio of 3.54 when the actual hazard ratio is 1.0. PASS statistical software (version 13.0) was used for calculation. For completeness, we acknowledge that the study has 80% power only for the specific set of conditions listed above and may lack canonical power when analyzing hypotheses involving secondary endpoints.

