#### **4.2 Statistical Analyses (Aim 1 only)**

The primary research hypothesis states that subjects receiving generic tacrolimus (Arm 2) would exhibit a 1-year survival rate non-inferior at a 26% margin to the rate among subjects receiving brand tacrolimus (Arm 1). The primary efficacy endpoint will be analyzed as time-to-event, with follow-up time measured in days, from the date of transplant to the date of composite endpoint. Statistical testing of time until composite event will be done for the intention-to-treat population. A Cox regression analysis (adjusting for transplant center via indicator variables) will be used to test the null hypothesis that  $H_0: HR \geq HR_0$  versus the alternative hypothesis  $H_1: HR < HR_0$  where  $HR_0$  is hazard ratio of the generic group over the brand group at the margin set at 3.54 (i.e., a 26% non-inferiority margin). The null hypothesis will be rejected if the upper bound of the 90% 2-sided confidence interval (corresponding to a 5% one-sided significance level) for HR is less than 3.54.

Secondary analyses are described next but all are considered exploratory since formal testing of hypotheses is considered dubious given the small sample sizes of stratified subjects. Additional Cox models that include indicator functions for the generic arm (with brand serving as baseline) and/or stratification based on age/race covariates will be used to estimate specific hazard ratios with 95% confidence intervals to evaluate differences among recipients in Arm 2 and risk groups. Also, individual analyses of single endpoint hazard ratios (graft rejection, failure, death) as well as point and interval estimates of group-specific survival rates at 1-year (via Kaplan-Meier and Greenwood methods) are planned without adjustment for multiple comparisons.

Standard descriptive summaries will also be used to report and compare adherence (as measured with daily medication diaries, and with the coefficient of variation of tacrolimus in subjects' blood) and immunologic endpoints (measured by the production of donor specific HLA antibodies).

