## 6.2 Study Therapy

**6.2.1 Clinical Sites:** Kidney recipients will be enrolled at UCLA, UCSD, UCI, UC Davis Medical Centers. Mechanistic studies will be performed utilizing specimens collected from all sites. Adherence will be measured with daily medication diaries, and with the coefficient of variation of tacrolimus in subjects' blood.

**6.2.2 References and comparator arms:** During phase 1 of study, following consent and randomization, the control group were prescribed brand tacrolimus and the comparator group was prescribed generic tacrolimus. The study drugs were prescribed upon discharge, but no later than 14 days after transplant. Subjects continued to receive study drug for up to one year post-transplant. During phase 2 of study, generic tacrolimus will only be prescribed as part of their regular care upon discharge but no later than 14 days after transplant.

**6.2.3 Provision of investigational drugs:** We anticipate that brand and generic tacrolimus will be provided for the entire study period for Phase 1 of the study. Generic tacrolimus will be obtained by the subject through their insurance for Phase 2 only. (See letters from Astellas - Appendix 5)

**6.2.4 Number of subjects and sample size justification:** We plan to enroll a total of 200 subjects between the four sites. Of the 200 kidney recipients at least 20 will be African American recipients. 40 randomized subjects will be on Brand and 160 subjects will be on generic.

**6.2.5 Eligible Subjects:** In Phase 1, eligible subjects will be initially randomized using a ratio of 2:1 (Brand:Generic) until 40 subjects have been enrolled into the brand medication arm (Arm 1) and 20 have been enrolled into the generic medication arm (Arm 2). In Phase 2, 140 additional eligible subjects will be enrolled without randomization onto generic tacrolimus only as part of their regular care. All subjects will be followed for 1-year post-transplant. (A split-phase randomization process is necessary due to a limited supply and narrow expiration-time window associated with the Brand medication product.)

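### If the primary Cox test pools both phases, any difference in event risk between Phase 1 and Phase 2 enters the generic/brand hazard ratio, in either direction, and the stated 5% level makes no allowance for it

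*Combined protocol and SAP*

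**What the plan says.** Section 4.2 gives one primary analysis: "A Cox regression analysis (adjusting for transplant center via indicator variables) will be used to test the null hypothesis" that the generic/brand hazard ratio is at or above the margin. Non-inferiority is declared when the upper limit of a two-sided 90% interval is below 3.54, which the section describes as "corresponding to a 5% one-sided significance level". No condition is attached. Age and race appear only in exploratory secondary models.

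On enrolment, Section 6.2.5 randomises 2:1 in Phase 1 until there are 40 brand and 20 generic subjects. After that, "In Phase 2, 140 additional eligible subjects will be enrolled without randomization onto generic tacrolimus only as part of their regular care". Section 3.1 says of Phase 2: "All subjects will be enrolled onto generic tacrolimus because they have elected to receive generic tacrolimus", this being the standard of care under their insurance. Section 6.2.7 confirms that Phase 2 has no randomisation.

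On who is analysed, the documents disagree:

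- Section 4.2 tests the intention-to-treat population. The Synopsis (statistical methods) defines this as randomised subjects with at least one dose of investigational drug. Section 3.5 adds that Phase 2 uses no investigational drug.
- Section 3.4 powers the trial on 50 brand and 150 generic subjects with 6 and 19 events. Section 6.2.8 sets Arm 2 at 160. Neither count can be reached without Phase 2 subjects.

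The documents contain no phase term, Phase 1-only analysis, comparison between phases, or sensitivity analysis by phase.

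**The concern.** Phase 2 has no brand subjects, so 140 of the 160 generic subjects (87.5%) have no concurrent randomised control. In a model with only product and centre, a difference in underlying risk between phases cannot be told apart from a product effect.

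The documents give reasons why the phases might differ. Phase 1 subjects accepted randomisation, while Phase 2 subjects enter on insurance-covered generic (3.1). The drug comes from study supply in Phase 1 and from the subject's pharmacy or hospital in Phase 2 (6.2.3, 7.3). The monitoring board serves Phase 1 only (3.5).

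What is at stake is the meaning of the result. A lower-risk Phase 2 makes a generic truly at the margin more likely to pass. A higher-risk Phase 2 makes a generic truly equal to brand more likely to fail. The plan attaches a fixed error rate to the rule and checks neither case.

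**Working it through.** **Inputs from the documents.** Margin: "hazard ratio of the generic group over the brand group at the margin set at 3.54" (4.2). Event rate: "Overall, 13% of subjects are expected to experience the primary endpoint by 1 year post-transplant" (3.4), so the brand hazard is −ln(0.87) = 0.139 per year. Power is calculated "when the actual hazard ratio is 1.0" (3.4). Dropout is 5% over 12 months (Table 1). Counts are 40 brand, and 20 + 140 generic (6.2.5). **Assumed input:** φ, the ratio of Phase 2 to Phase 1 underlying hazard. The documents give no value, so a range is shown.

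**1. The plan's own figures.**
- Margin: 0.87^3.54 = 0.611, which matches 61% in Table 1.
- Events, with 5% dropout spread over the year: 50 × 0.13 × 0.975 = 6.3 and 150 × 0.13 × 0.975 = 19.0, which matches 6 and 19.
- Power (Schoenfeld, one-sided 0.05, 25 events, 50:150): Φ(ln 3.54 × √(25 × 0.25 × 0.75) − 1.645) = Φ(2.737 − 1.645) = 86%. At 40:160: Φ(2.528 − 1.645) = 81%. Both agree with the stated power above 80%.

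The stated event count is therefore reached only with Phase 2 subjects in the test.

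**2. How a phase shift enters the hazard ratio.** With true product ratio θ, the average generic hazard relative to brand is roughly θ × (20 + 140φ)/160 = θ × (0.125 + 0.875φ). For a generic at the margin (θ = 3.54):
- φ = 0.85: 3.54 × 0.869 = 3.08
- φ = 0.70: 3.54 × 0.738 = 2.61
- φ = 1.15: 3.54 × 1.131 = 4.00

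**3. Simulated false non-inferiority.** Exponential event times, censoring at 1 year, true hazard ratio 3.54 in both phases, 40 brand v 20 + 140 generic, Cox fit, success if the upper 90% Wald limit is below 3.54. The ranges cover separate runs of 6,000 to 40,000 trials, with and without dropout and, at some values of φ, with centre indicators.

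| φ (assumed) | False non-inferiority |
|---|---|
| 1.15 | 3.1–3.3% |
| 1.00 | about 6% |
| 0.90 | 8.7–9.0% |
| 0.85 | 10.0–11.0% |
| 0.80 | 12.8–13.3% |
| 0.70 | 18–19% |
| 0.50 | 34–36% |

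The rate at φ = 1 is already above 5% because brand contributes only 40 × 0.13 = 5.2 expected events. At φ = 0.85 the phase effect is thus a move from about 6% to about 10.5%.

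Closed-form check at φ = 0.85: SE = √(1/5.2 + 1/(160 × 0.389)) = 0.456, and Φ(−1.645 + 0.875 × 0.1625/0.456) = 9.1%. Other choices of SE give 8.7% to 12.0%.

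**4. Power at a true hazard ratio of 1.** The simulated pooled 40:160 test has about 72% power at φ = 1 and 62–64% at φ = 1.25.

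**5. Randomised subjects only.** Phase 1 alone (40 v 20) gives an error of 4.6–5.0% and power of about 43–45%. A phase-indicator model on all subjects (run at φ = 0.85 for the error) gives 4.5% and about 42%. The power figures count a trial with no Phase 1 generic event as a failure. That happens in 0.87^20 = 6.2% of trials before dropout and about 7% with it. Power reaches about 50% only if those trials count as successes.

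**6. What a tipping point looks like.** At 5.2 v 20.8 events and an estimated ratio of 1, the upper limit is exp(1.645 × √(1/5.2 + 1/20.8)) = 2.24. Solving 1/(0.125 + 0.875φ) = 3.54/2.24 gives φ of about 0.58.

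**The case against.** The strongest reply is that the problem may not arise. Read literally, the Synopsis definition confines the primary test to 40 v 20 randomised, concurrent subjects, and there is no phase confounding. This stands as far as it goes: the concern is conditional on pooling. But the event count in 3.4 and the arm size in 6.2.8 require pooling, so the plan has to choose.

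Second, a reader might infer that the error rate is doubled, or that the design favours generic. The documents support neither. The 15% fall is an assumption, about one percentage point of the excess over 5% exists with no shift, and a 15% rise lowers the rate to about 3%.

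Third, the reference to electing generic suggests that healthier patients chose it over brand. Phase 2 offers no brand option, and Section 6.2.5 attributes the split to brand supply and expiry. Eligibility criteria, centres and trough targets are shared, and enrolment is planned within 12 months. These points limit the plausible shift but do not exclude one.

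Fourth, Section 4.1 records many risk factors, including donor type, cold ischaemic time, PRA and induction. They could explain part of a phase difference. The primary model uses none of them, and they cannot cover unrecorded differences in who enrols.

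Finally, the expected result would tip only at a fall of about 42%. That is reassuring for that one result. It is also a reason to report the tipping point, since a less favourable estimate would tip sooner.

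**Conclusion.** The concern holds if the primary test pools both phases, as the sample size and arm sizes imply. The unconditional 5% level is then not supported. It is about 6% with no phase difference, and across assumed phase ratios from 1.15 down to 0.70 it runs from about 3% to about 19%. Loss of power is the corresponding risk when Phase 2 carries higher risk.

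These sizes rest on exponential event times, 13% brand events at one year, 40 v 20 + 140 subjects, and a phase effect common to both products. Nothing in the documents shows that a shift will occur, how large it would be, or in which direction. Nor is a phase term a free repair: Phase 2 has no brand subjects, so once the term is added the product effect comes from the 40 v 20 alone.

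**What to change.** 1. **Reconcile the analysis population first.** The Synopsis definition (randomised and dosed: 40 v 20, about 43–45% power) and the counts in 3.4 and 6.2.8 cannot both stand. Align related statements at the same time: 50/150 in 3.4 against 40/160 in 6.2.4; 6.2.8, which describes both arms as randomised; and 3.1, which starts Phase 2 after 40 Phase 1 subjects where 6.2.5 implies 60.
2. **If the pooled test stays primary**, describe it in 4.2 as a partly non-randomised comparison. State that its error rate is about 6% with no phase difference and is not controlled at 5% if event risk differs between phases.
3. **Pre-specify supportive analyses**, reported beside any non-inferiority conclusion:
   - the generic/brand hazard ratio with 90% interval from randomised Phase 1 subjects, or from the primary Cox model with a phase indicator added;
   - the Phase 2 v Phase 1 hazard ratio among generic subjects;
   - a two-sided tipping-point analysis, refitting the primary model with a fixed offset ln(φ) for Phase 2 subjects, with φ below and above 1, and reporting the φ at which the conclusion changes.

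The cost is SAP wording and a few model fits on data already collected, with no more patients. The downsides are that the phase-adjusted estimate is imprecise (about 43% power, with about 7% of trials having no Phase 1 generic event), so it can only be supportive, and that the stated error rate becomes less favourable. These additions do not restore 5% control of the pooled test; they show how far its conclusion depends on the phases being alike.

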### **5.0 SUBJECT SELECTION CRITERIA**

Recruitment: No recruitment flyers will be used in the study, as subjects will be recruited in person during their primary hospitalization after transplant or during their pre-transplant visit. For entry into the study, all subjects must meet the following criteria.

#### **5.1 Inclusion Criteria**

1. Signed informed consent and/or assent
2. Between the ages of 18 and 70 years, inclusive

3. Current or future kidney transplant recipients, no more than 14 days after transplant and prior to hospital discharge. Inclusion of future kidney transplant recipients cannot exceed 30-days pre-transplant.
4. Able to swallow tablets and capsules at the time of randomization
5. Subjects must be receiving a primary or secondary kidney allograft from a deceased donor or from a non- HLA identical living donor
6. Negative cross match test, and compatible (A, B, AB or O) blood type
7. Subjects must have no known contraindications to tacrolimus
8. Women of childbearing potential (WOCBP) must have a negative pregnancy test and be willing to use 2 methods of contraception during the study and for 6 weeks after stopping the study drug.

WOCBP includes any female who has experienced menarche and who has not undergone successful surgical sterilization (hysterectomy, bilateral tubal ligation, or bilateral oophorectomy) or is not postmenopausal (defined as amenorrhea  $\geq$  12 consecutive months; or women on hormone replacement therapy with documented serum follicle stimulating hormone level  $>$  35 mIU/cc). Women who are using oral, implanted, or injectable contraceptive hormones (intrauterine device), mechanical products or barrier methods (diaphragm, condoms, spermicides), are practicing abstinence, or have a sterile partner (e.g., vasectomy), will be considered of child bearing potential.

In addition, WOCBP who are taking MMF must use methods of birth control as stipulated in the package insert, namely:

Either intrauterine device, or partner with vasectomy, or one hormone (oral contraceptive pill, transdermal patch, vaginal ring, or progesterone injection or implant) and one barrier method (diaphragm or cervical cap with spermicide, contraceptive sponge, or male or female condom), or two barrier methods as described above.

WOCBP must have a negative serum pregnancy test (minimum sensitivity 25 IU/L or equivalent units of human chorionic gonadotropin [HCG]) at the time of transplant.

## **5.2 Exclusion Criteria**

1. Those who receive simultaneous combined organ transplants
2. Subjects with clinically significant active infections (for example, those requiring hospitalization, or as judged by the Investigator) or malignancies
3. Recipients who are concurrently receiving belatacept or anticipate to receive belatacept as part of their immunosuppressive regimen
4. Subjects currently enrolled in another investigational device or drug study
5. WOCBP who are unwilling or unable to use an acceptable method to avoid pregnancy for the entire study period and for 6 weeks after stopping the study drug
6. Women who are breast-feeding or pregnant with a positive pregnancy test on enrollment or prior to study drug administration
7. Prisoners or subjects who are compulsorily detained (involuntarily incarcerated) for treatment of either a psychiatric or physical (e.g., infectious disease) illness must not be enrolled into this study.
8. Any psychiatric or medical condition that, in the investigator's opinion, may put the subject at significant risk, may confound the study results, or may interfere significantly with the subject's participation in the study.

## **6 STUDY CONDUCT**

## 6.1 Ethics

This study will be conducted in accordance with the ethical principles that have their origin in the current Declaration of Helsinki, and will be consistent with International Conference on Harmonization Good Clinical Practice (ICH GCP) and applicable regulatory requirements.

The study will be conducted in compliance with the protocol. The protocol and any amendments and the subject informed consent will receive Institutional Review Board (IRB) approval prior to initiation of the study.

Freely given written informed consent must be obtained from every subject or their legally authorized representative prior to clinical trial participation, including informed consent for any screening procedures conducted to establish subject eligibility for the trial.

For further details on informed consent, see Section 10.2.

The rights, safety and well-being of the trial subjects are the most important considerations and should prevail over interests of science and society.

Study personnel involved in conducting this trial will be qualified by education, training, and experience to perform their respective task(s).

This trial will not use the services of study personnel where sanctions have been invoked or where there has been scientific misconduct or fraud (e.g., loss of medical licensure, debarment).

Systems with procedures that assure the quality of every aspect of the study will be implemented.

## 6.2 Study Therapy

**6.2.1 Clinical Sites:** Kidney recipients will be enrolled at UCLA, UCSD, UCI, UC Davis Medical Centers. Mechanistic studies will be performed utilizing specimens collected from all sites. Adherence will be measured with daily medication diaries, and with the coefficient of variation of tacrolimus in subjects' blood.

**6.2.2 References and comparator arms:** During phase 1 of study, following consent and randomization, the control group were prescribed brand tacrolimus and the comparator group was prescribed generic tacrolimus. The study drugs were prescribed upon discharge, but no later than 14 days after transplant. Subjects continued to receive study drug for up to one year post-transplant. During phase 2 of study, generic tacrolimus will only be prescribed as part of their regular care upon discharge but no later than 14 days after transplant.

**6.2.3 Provision of investigational drugs:** We anticipate that brand and generic tacrolimus will be provided for the entire study period for Phase 1 of the study. Generic tacrolimus will be obtained by the subject through their insurance for Phase 2 only. (See letters from Astellas - Appendix 5)

**6.2.4 Number of subjects and sample size justification:** We plan to enroll a total of 200 subjects between the four sites. Of the 200 kidney recipients at least 20 will be African American recipients. 40 randomized subjects will be on Brand and 160 subjects will be on generic.

**6.2.5 Eligible Subjects:** In Phase 1, eligible subjects will be initially randomized using a ratio of 2:1 (Brand:Generic) until 40 subjects have been enrolled into the brand medication arm (Arm 1) and 20 have been enrolled into the generic medication arm (Arm 2). In Phase 2, 140 additional eligible subjects will be enrolled without randomization onto generic tacrolimus only as part of their regular care. All subjects will be followed for 1-year post-transplant. (A split-phase randomization process is necessary due to a limited supply and narrow expiration-time window associated with the Brand medication product.)

**6.2.6 Screening, recruiting and eligibility:** All Kidney recipients that are 1) less than 30 days pre-transplantation or 2) up to 14 days post-transplantation, but prior to discharge, who are deemed a candidate for a tacrolimus immunosuppression regimens and meet the inclusion and exclusion criteria above, are eligible for the study. They will be invited to participate and given written informed consent for enrollment. We will attempt to enroll all subjects in a 12-month time period.

**6.2.7 Study enrollment and randomization:** This randomized, prospective, open-labeled, 2-group, parallel observational study will enroll a total of 200 subjects across 4 clinical sites. During phase 1 of the study, randomization was done after the informed consent process, using a block system pre-generated by a computer and stratified by site, ethnic group, and age cohort. During phase 2 of the study, no randomization will occur, and all subjects will be placed onto standard of care generic tacrolimus.

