### **2.2 Secondary Objectives**

Will compare in the brand versus generic arms:

- Graft rejection at 1 year after transplant
- Graft failure at 1 year after transplant
- Death at 1 year after transplant
- Loss-to-follow-up at 1 year after transplant
- Incidence of infectious episodes at 1 year after transplant
- Incidence of malignancy at 1 year after transplant
- Adherence with medication regimen

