### **6.2.9 Study Visits and Post randomization follow-up**

A total of 7 visits, over a 12-month period, are planned as follows. All subjects will continue to receive routine labs as part of their standard of care from their treating physician. For detailed information about the study labs schedule see Table 5 Study Schedule. Safety labs are done as part of their standard of care from their treating physician.

Subjects on Phase 1 who need more study drug medication before his or her next study visit, will receive a new supply from clinic. Subjects on Phase 2 will receive drug from their pharmacy/hospital.

**First (Baseline) Visit** (up to 14 days after transplant but before the study subject is discharged from the hospital):

- Subject reviews and signs consent form
- Review of subject's medical history
- Review of subject's current medications
- Review of subject's physical exam including vital signs (blood pressure, temperature, pulse and respiration rate), height and weight
- Review of clinical labs
- Randomization of subject in Phase 1 only
- Subject will receive drug at discharge.

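### The brand-versus-generic adherence comparison mixes product with study phase: all 40 brand subjects are on study-provided drug, while 140 of 160 generic subjects are non-randomised and supplied through insurance

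*Combined protocol and SAP*

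**What the plan says.** **Who is in each arm.** Section 6.2.4 plans that "40 randomized subjects will be on Brand and 160 subjects will be on generic". Section 6.2.5 explains how this total is reached. Phase 1 randomises 2:1 "until 40 subjects have been enrolled into the brand medication arm (Arm 1) and 20 have been enrolled into the generic medication arm", and then "140 additional eligible subjects will be enrolled without randomization onto generic tacrolimus only". Section 3.1 adds that Phase 2 subjects are on generic because they chose it, as their insurer's standard of care.

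**How the drug is supplied.** For Phase 1, section 6.2.3 says: "We anticipate that brand and generic tacrolimus will be provided for the entire study period for Phase 1 of the study". For Phase 2 it says: "Generic tacrolimus will be obtained by the subject through their insurance for Phase 2 only". Section 6.2.9 sends Phase 1 subjects who run short to the clinic, whereas "Subjects on Phase 2 will receive drug from their pharmacy/hospital". Sections 7.3 and 8.2 repeat the insurance route for Phase 2.

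**What is compared.** Section 2.2 lists "Adherence with medication regimen" among the objectives to be compared between the brand and generic arms. Section 4.2 says: "Standard descriptive summaries will also be used to report and compare adherence". The measures are daily diaries and the coefficient of variation (CV) of tacrolimus levels (sections 3.3, 4.2 and 6.3). None of these sections restricts the comparison to Phase 1, splits it by phase or adjusts it for supply route. The descriptive analysis of the generic supplied, promised after Table 1, does not mention route.

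**The concern.** Brand exists only in Phase 1, so supply route nearly coincides with product. How a subject obtains the drug (dispensed at study visits, or filled through a pharmacy or hospital) is a plausible direct influence on missed doses, so it bears on adherence more than on most endpoints. Route is not the only factor tied to phase. Phase 2 subjects were not randomised, elected generic and enrol in a later period, and section 6.2.9 marks the return of leftover drug as Phase 1 only.

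A pooled brand-generic difference in adherence would naturally be read as a property of the product. Phase differences alone could create such a difference, or hide a real one, and enrolling more Phase 2 subjects would not reduce the problem. The 20 generic subjects who share the brand arm's conditions are outnumbered seven to one within their own arm.

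**Working it through.** **1. Counts.** From section 6.2.5: Phase 1 has 40 brand and 20 generic subjects, and Phase 2 has 140 generic. Then 20 + 140 = 160 generic and 40 + 160 = 200 in total, which reproduces section 6.2.4. The documents give no effect size, standard deviation or power for adherence, so there is no further figure of the plan's to reproduce.

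**2. Share supplied through insurance.** Brand: 0/40 = 0%. Generic: 140/160 = 87.5%.

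**3. Effect on the pooled comparison.** Suppose the products are identical, mean adherence in Phase 1 is m in both arms, and Phase 2 conditions lower it by d (a negative d would raise it).
- Brand mean: m
- Pooled generic mean: [20m + 140(m − d)]/160 = m − 0.875d
- Brand minus generic: 0.875d, with no product effect at all

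Here d is the whole Phase 2 shift, from route and from anything else that goes with phase. The documents do not give it. For illustration only:

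| Assumed d (SD) | Spurious difference 0.875d (SD) |
|---|---|
| 0.1 | 0.09 |
| 0.2 | 0.18 |
| 0.3 | 0.26 |
| 0.5 | 0.44 |

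**4. Sensitivity to the conflicting counts.** Other sections disagree with 6.2.5.
- Section 3.1 starts Phase 2 once 40 subjects in total are in Phase 1. At 2:1 that is about 27 brand and 13 generic. With the total kept at 200, Phase 2 has 160 subjects, and 160/(160 + 13) = 92% of generic subjects are insurance-supplied.
- Section 3.4 powers on 50 brand and 150 generic. If the 2:1 ratio held (an assumption), Phase 1 would have 25 generic subjects and Phase 2 would have 125, and 125/150 = 83%.

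The imbalance is large on every reading, and larger than 87.5% under section 3.1.

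**5. Precision of the Phase 1 contrast.** In SD units, with equal SDs assumed:
- Pooled, 40 v 160: SE = √(1/40 + 1/160) = 0.177, 95% half-width 1.96 × 0.177 = 0.35
- Phase 1, 40 v 20: SE = √(1/40 + 1/20) = 0.274, 95% half-width 1.96 × 0.274 = 0.54
- Ratio: 0.274/0.177 = 1.55

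**The case against.** The strongest reply is that adherence is exploratory and descriptive. Section 4.2 calls formal testing of secondary endpoints dubious and specifies no test or interval for adherence. That stands, and it limits how serious the point is. It does not remove the point, because a two-column descriptive table headed brand and generic is still read as a product comparison.

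A second reply is that section 3.1 attaches the two arms to Phase 1, so the comparison in section 2.2 might already mean Phase 1 only. Section 6.2.8, however, gives Arm 2 as n = 160, which includes Phase 2. At best the text is ambiguous.

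A third is that insurance supply reflects ordinary practice. It does so for generic only. A practice-based comparison would need both products on that route.

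A reader might infer more than the documents support:
- *That Phase 2 subjects pay for their drug and that cost lowers adherence.* The text says only that the drug is obtained through insurance. It states no out-of-pocket cost, and section 8.2 includes supply during admission and clinic contacts, which softens the contrast between clinic and pharmacy.
- *That the plan carries a calculable false-positive rate for adherence.* It specifies no interval to exclude zero, and nothing in it anchors d.
- *That Phase 1 is free of route differences by design.* Phase 1 provision is worded as an expectation, and section 8.2 does not state the source of Phase 1 generic.
- *That Phase 1 generic against Phase 2 generic would measure the route effect.* Those groups also differ in randomisation, election of generic and enrolment period.
- *That this adherence argument undermines the primary test.* It does not address that test.

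**Conclusion.** The point holds for the adherence comparison. As planned, it cannot separate product from supply route, self-selection and enrolment period. On the section 6.2.5 counts, 87.5% of any Phase 2 shift in mean adherence appears as a brand-generic difference (0.875d). The multiplier rests on those counts, on a comparison of means and on Phase 1 provision happening as anticipated. The size and direction of d are unknown. The multiplier applies to either measure if it is summarised by a mean, but the documents do not show whether phase or route affects the tacrolimus CV as it might affect diary adherence. Because the endpoint is secondary and exploratory, this is a weakness of analysis and reporting that should be corrected, and it can be corrected with data already being collected.

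**What to change.** In sections 4.2 and 6.3:
1. Tabulate diary adherence and tacrolimus CV in three groups: Phase 1 brand, Phase 1 generic and Phase 2 generic.
2. Base any brand-versus-generic statement about the product on the randomised Phase 1 contrast (40 v 20).
3. Describe Phase 1 generic against Phase 2 generic as a combined phase difference (supply route, self-selection, enrolment period), not as a supply-route effect.
4. Reconcile the Phase 1 and arm sizes in sections 3.1 and 3.4 with 6.2.4 and 6.2.5, so that the group sizes are stated once.

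The change is to wording only and needs no new data. The price is precision: the standard error of the product contrast becomes 0.274 SD in place of 0.177 SD, about 1.55 times as large. No stated power is lost, since none is claimed for adherence.
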